# I. BACKGROUND AND SIGNIFICANCE

Drug resistant epilepsy is a serious and potentially life-threatening condition that impacts the day to day functioning of those affected. Patients with drug resistant epilepsy are at a higher risk for Sudden Unexpected Death in Epilepsy (SUDEP), as frequency of generalized tonic-clonic seizures, poly therapy, number of anti-epileptic drugs (AED) used, and propensity for nocturnal seizures are the leading risk factors for SUDEP. Annual SUDEP risk for patients with epilepsy is 1/1000; whereas SUDEP risk for patients with drug resistant epilepsy is 1/150.

Patients with drug resistant epilepsy do not respond or respond incompletely to FDA approved AEDs. Children living with drug resistant epilepsy are particularly vulnerable, and urgently need more effective medications because those suffering from early-onset and high seizure burden epilepsies suffer the greatest neurodevelopmental problems, including intellectual disability and autism. In some syndromes such as Dravet Syndrome, recent evidence suggests that more effective early control of epilepsy is associated with better developmental outcomes than in children who were treated 20-30 years ago (Chieffo et al., 2011).

Sunflower Syndrome (also referred to as Self-induced Photosensitive Epilepsy) is a rare epileptic disorder characterized by a distinctive seizure that manifests itself in a highly stereotyped physical behavior. Seizure types associated with Sunflower Syndrome include absence seizures and generalized tonic-clonic seizures. Associated with these seizures, individuals with Sunflower Syndrome obsessively seek out a light source, stare at the light source, and wave one hand in front of their eye (Belcastro & Striano, 2014; Ames, 1971; Aicardi & Gastaut, 1985). Electroencephalogram (EEG) features include generalized spike and wave discharges interictally, and typically a strong photoparoxysmal response during photic stimulation (Belcastro & Striano, 2014; Ames & Saffer,

Detailed Protocol Version Date 02/21/2020 1

Currently, Sunflower Syndrome is poorly characterized in scientific literature and often misunderstood at the clinical level. The name selfinduced photosensitive epilepsy may be a misnomer as research concerning the neurochemical and neuropsychological pathways have not been enough to truly characterize it as a self-induced (conscious behavior) as the name implies. Although some reports have concluded that the hand waiving induces the seizure, these findings are not consistent throughout scientific literature (Belcastro & Striano, 2014; Livingston & Torres, 1964). In fact, an EEG report found that the seizures can begin prior to the hand waving. This suggests that the hand waving may in fact be part of the seizure, not the cause (Livingston & Torres, 1964).

# Preclinical Data:

Fenfluramine has been studied in young rats. In those neurochemical experiments, fenfluramine was shown to reduce activity and to induce learning and memory deficits. Fenfluramine was also shown to reduce certain chemicals in the brain, including serotonin, but the long-term effects of this are not known (Fuller, Snoddy, & Robertson, 1988).

The relevance of the animal data to humans is not known. Not many learning and memory studies have been conducted with fenfluramine in humans.

# **Clinical Data: Fenfluramine in Epilepsy**

Aicardi and Gastaut wrote a letter to the NEJM in 1985 describing the successful use of fenfluramine in 3 children with self-induced photic sensitive epilepsy. The description of the first of the three patients matches that of Sunflower Syndrome (Aicardi & Gastaut, 1985). Additionally, there have been several published reports of fenfluramine's successful treatment of refractory childhood epilepsy in the 1980's, as well as, its successful treatment of 11 pediatric patients with refractory or self-induced epilepsy, not specifically Sunflower Syndrome, in Belgium.

In 1996, a Belgian group reported on the use of fenfluramine in 11 children, ages 18 months to 15.5 years old, with refractory or self-induced epilepsy (Boel & Casaer, 1996). Subjects were treated with fenfluramine at 0.5 to 1.0 mg/kg/day for 3 to 8.5 years. Sixty four percent of the subjects became seizure free and the remaining 36% of subjects experienced greater than or equal to 75% reduction in seizure frequency. By 2002, this study's population had been expanded to 22 patients with intractable or self-induced seizures who underwent

treatment between 1 to 12 years. Of the 22 patients treated, 27% (6) became seizure-free, 45% (10) patients had a 90% reduction in seizure frequency and 27% (6) patients were non-responders.

Zogenix, Inc. is currently evaluating fenfluramine hydrochloride (ZX008) in Dravet Syndrome (DS) in three Phase 3 double-blind, randomized, placebo-controlled studies, in which our site participated. Dravet Syndrome is a rare form of refractory epilepsy, which exhibits similar seizure types, as those seen in Sunflower Syndrome. This study enrolled 119 subjects across sites in the United States, Canada, Europe, and Australia. "The median age of subjects was 8 years (range, 2-18 years). Following a six-week baseline observation period, subjects were randomized to one of three treatment groups: ZX008 0.8 mg/kg/day (30 mg maximum daily dose; n=40), ZX008 0.2 mg/kg/day (n=39) and placebo (n=40) in which ZX008 or placebo was added to current regimens of antiepileptic drugs. Subjects were titrated to their target dose over two weeks and then remained at that fixed dose for 12 weeks. The mean baseline convulsive seizure frequency across the study groups was approximately 40 seizures per month.

The primary efficacy measure was a comparison of the change in mean monthly convulsive seizure frequency between ZX008 0.8 mg/kg/day and placebo during the 14-week treatment period compared with the 6-week baseline observation period. Subjects taking ZX008 0.8 mg/kg/day achieved a 63.9% reduction in mean monthly convulsive seizures compared to placebo (p<0.001). The median percent reduction in monthly convulsive seizure frequency was 72.4% among ZX008 0.8 mg/kg/day subjects compared to 17.4% in placebo subjects.

A key secondary endpoint was the same analysis for a comparison of ZX008 0.2 mg/kg/day and placebo. Subjects taking ZX008 0.2 mg/kg/day achieved a reduction in mean monthly convulsive seizures of 33.7% compared to placebo (p=0.019). Collectively, these top-line data suggest a dose-response relationship for ZX008 in the adjunctive treatment of convulsive seizures in Dravet syndrome" ("Zogenix Announces Positive Top-line Results from Pivotal Phase 3 Clinical Trial of ZX008 in Dravet Syndrome", September 2017).

There are no treatments specifically approved for the treatment of Sunflower Syndrome in the United States. Broad spectrum anticonvulsant medications, including sodium valproate, lamotrigine, levetiracetam, and clobazam, have not shown full efficacy in seizure prevention in patients with Sunflower Syndrome. Accordingly, there remains a significant unmet need for an approved treatment for children and adults with Sunflower Syndrome.

As this epilepsy typically does not respond to anticonvulsant medications, and since Aicardi described the successful treatment with fenfluramine of at least one child with this syndrome, we would like to investigate if fenfluramine is an effective, safe and well tolerated treatment for Sunflower Syndrome.

# **II. SPECIFIC AIMS**

The primary objective of this study is the determine the efficacy of ZX008 on seizure frequency in children and young adults with Sunflower Syndrome. The goal of treatment is to provide a 30 percent or greater reduction of generalized tonic-clonic seizures and/or hand waving associated with absence seizures.

Secondary objectives of the study include evaluation of the effect of ZX008 (fenfluramine hydrochloride) on EEG patterns and quality of life. Patients with Sunflower Syndrome often experience low self-esteem, bullying due to the unusual motor movements associated with their seizures, school performance issues, anxiety, and depression.

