# **III. SUBJECT SELECTION**

The study population will include pediatric and young adult patients seen by [name]., Ph.D. at MGH's Pediatric Epilepsy Clinic who were identified as candidates. The Principal Investigator (PI) will follow up to 20 patients with Sunflower Syndrome who will be taking ZX008.

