# **V. STUDY PROCEDURES**

The investigational drug to be used in this study is fenfluramine hydrochloride (ZX008) manufactured by Zogenix, Inc..

ZX008 will be supplied as an oral solution in a concentration of 2.5 mg/mL. The subjects will be treated on an outpatient basis and will not require hospital admission. ZX008 will be administered on a twice daily basis.

The study will initially consist of a 4 week baseline period, during which handwaving associated with absence seizures and/or generalized tonic-clonic seizures will be recorded in a seizure diary on a daily basis. Subjects will meet enrollment criteria if they have an average of 6 generalized tonic-clonic and/or handwaving associated absence seizure per week.

If enrollment criteria is met, the subject will enter a titration period. The starting dose will be 0.2 mg/kg/day for the first 14 days. The dose will be increased every 2 weeks as tolerated by 0.2 mg/kg/day, to a maximum dose of 0.8 mg/kg/day, or a total maximum dose of 30 mg/day. The subject will remain on 0.8 mg/kg/day, 30 mg/day, or maximum tolerated dose for a 6 week maintenance period.

Site personnel will call the subject and/or their parent/caregiver every 11-14 days during the titration period before their next scheduled dose increase.

There will be 5 study visits within a 6 month period. After Visit 5, visits will occur every 6 months for an assessment in the clinic for subjects who respond to treatment with at least a 30% reduction in seizure frequency.

Seizure frequency will be tracked with the use of a daily seizure log. In the event that seizure frequency is markedly reduced compared to baseline after starting the study drug the LPI will discuss with the subject and/or their caregiver about adjusting the dose of concomitant seizure medications. If seizure frequency is markedly increased compared to baseline after discontinuing other medications which were taken as standard of care the LPI may decide to adjust dose of other seizure medications or reintroduce the medications that were taken as

IND Visit Schedule					
Visit Number	Visit Type	Time Point			
1	Baseline	Day -28			
2	Titration	Day 1 (+14 days)			
3	Titration and/or	28 days from Visit 2			
	Maintenance	(±7 days)			
4	Maintenance	56 days from Visit 2			
		(±14 days)			
5	Maintenance	84 days from Visit 2			
		(±14 days)			
Continuous	Maintenance	Each 6 Months			
		following Visit 5			
		(±14 days)			

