#### Level 3:

1. The principal investigator will evaluate efficacy to date based on study diaries and consult with the parent/guardian, and determine whether the achieved benefit justifies the consideration of continuing study treatment. MINIMAL efficacy criteria for consideration:

- a. Seizures must be more than 75% improved (number of convulsive seizures per 28 days) on treatment over baseline, and improvement must be consistent.
- b. The number, type, duration, and distribution of seizures at baseline should be of a severity, which justifies the risks of cardiopulmonary complications, considering the subject's age and overall health.
- c. Subject has had reasonable trials (dose and duration) of other available anticonvulsants, alone or in combination, and not maintained the level of seizure control achieved with study medication.
- 2. If the principal investigator feels consideration of continued treatment is warranted considering benefit and potential risk, and the parent/guardian feels strongly that the child be maintained on the study medication when understanding the risks, the parent/guardian must sign a statement acknowledging their understanding of the positive findings and possible risks associated with continuing in the study. The child should provide assent if appropriate. If both of these conditions are not met, the subject is discontinued from treatment.
- 3. The principal investigator prepares a case history and rationale for continuation to review with the local cardiologist, including consideration of effects on seizures and comorbidities.
- 4. The principal investigator and local cardiologist will evaluate the risks and proposed monitoring plan, if applicable.
- 5. The principal investigator and local cardiologist will make a determination of appropriate path, including these possible outcomes:
  - a. Discontinue study medication
  - b. Increase frequency of ECHO and ECG monitoring
  - c. Add additional ECG and/or ECHO measures to be monitored
  - d. Reduce the dose of study medication

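### Does the primary objective claim more efficacy than one uncontrolled arm of at most 20 patients can show?

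*Protocol*

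**What the plan says.** Section II (Specific Aims) gives the primary objective: "The primary objective of this study is the determine the efficacy of ZX008 on seizure frequency in children and young adults with Sunflower Syndrome". The next sentence adds: "The goal of treatment is to provide a 30 percent or greater reduction of generalized tonic-clonic seizures and/or hand waving associated with absence seizures".

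Section III describes the whole study group in one line: the investigator "will follow up to 20 patients with Sunflower Syndrome who will be taking ZX008". No control group, randomisation or blinding is described anywhere for this study.

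Section V (Study Procedures) sets a 4-week diary baseline, a titration period and a 6-week maintenance period. The baseline diary also decides entry: "Subjects will meet enrollment criteria if they have an average of 6 generalized tonic-clonic and/or handwaving associated absence seizure per week". Visits after Visit 5 are for "subjects who respond to treatment with at least a 30% reduction in seizure frequency".

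A stricter mark appears only in Section VII, as a condition for considering continued treatment after a Level 3 echocardiogram finding: "Seizures must be more than 75% improved (number of convulsive seizures per 28 days) on treatment over baseline, and improvement must be consistent".

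The background section closes more softly: "we would like to investigate if fenfluramine is an effective, safe and well tolerated treatment for Sunflower Syndrome".

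**The concern.** A before-after comparison in a single arm mixes the drug's effect with whatever would have happened anyway. Two features of this design sharpen the point. A 30% fall is a modest change for a count that may fluctuate. And the diary that admits a patient is also the pre-treatment reference, so a patient who enters on an unusually bad month will tend to look better later.

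The protocol itself shows that seizure counts can fall without the drug: the Dravet trial cited in the background had a median fall of 17.4% on placebo.

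If 8 or 10 of 20 patients reached the 30% mark, a reader of the objective might take this as efficacy shown, although it could be background. That would matter for a drug with known valve and pulmonary-hypertension risks and for a syndrome without an approved treatment.

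**Working it through.** **What there is to reproduce.** The protocol gives no alpha, power, assumed responder share, background share or variance. The ceiling of 20 therefore has no calculation behind it to check. The question is whether the stated objective needs something the design cannot give.

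**Inputs from the protocol.** At most 20 patients (Section III); 4-week baseline, 6-week maintenance and entry at 6 per week, which is 6 × 4 = 24 per 28 days (Section V); 30% mark (Sections II and V); placebo median fall 17.4% in Dravet syndrome, and 6 seizure-free plus 10 with a 90% fall out of 22 in the larger earlier series (background section).

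**Inputs assumed, not documented.** Median true rate M of 24 to 160 per 28 days; between-patient log-SD 0.5; independent drift of each patient's rate in each period with log-SD s; no drug effect.

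**Step 1: share with a fall of at least 30% and no drug effect.** Baseline count ~ Poisson(rate × exp(s·z1)), kept if 24 or more. Maintenance count ~ Poisson(1.5 × rate × exp(s·z2)), divided by 1.5. A responder has maintenance/baseline ≤ 0.70. Simulated shares in %:

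| s | M = 24 | M = 40 | M = 80 | M = 160 |
|---|---|---|---|---|
| 0 (Poisson only) | 8.9 | 4.6 | 1.3 | 0.2 |
| 0.3 | 33.0 | 26.0 | 21.9 | 20.8 |
| 0.5 | 46.5 | 38.1 | 32.5 | 31.1 |
| 0.7 | 54.4 | 45.7 | 39.0 | 36.5 |

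A closed form for high rates, ignoring Poisson noise and selection, agrees with the last column. The share is Φ(ln 0.70 / (s√2)), with ln 0.70 = −0.357:
- s = 0.3: Φ(−0.84) = 20%
- s = 0.5: Φ(−0.50) = 31%
- s = 0.7: Φ(−0.36) = 36%

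So s drives the answer, and the protocol says nothing about s.

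**Step 2: effect of entry selection.** Without the threshold, the s = 0.5 row becomes 31.9, 31.5, 31.1 and 30.9. Selection adds 46.5 − 31.9 = 14.6 points at M = 24 but only 31.1 − 30.9 = 0.2 points at M = 160. The M = 24 column, which supplies every upper end, assumes that half of all candidates have a true rate below the entry threshold.

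**Step 3: plausibility of s = 0.7.** The log ratio of two periods then has SD 0.7 × √2 = 0.99. The chance of at least doubling or halving with no drug effect is 2Φ(−0.693/0.99) = 2Φ(−0.70), about 48%. That is a strong assumption where epilepsy treatment must be stable for 4 weeks before screening and is expected to remain so until Month 3 (Section III).

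**Step 4: what results of 20 would exclude.** Exact (Clopper-Pearson) lower 95% limit = the 0.025 quantile of Beta(x, n − x + 1):
- 8/20: 19.1%. Clears the background until s exceeds 0.16 to 0.28, depending on M.
- 10/20: 27.2%. Clears it until s exceeds 0.24 to 0.41.
- 16/20: 56.3%. Clears every cell in the table.
- 16/22, the larger earlier series: 49.8%. Clears every cell except 54.4% (M = 24, s = 0.7).

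The series result counts falls of 90% or seizure freedom, so a 75% mark is the fairer comparison. Its highest modelled background is 15.7%, which 49.8% clears easily.

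**Step 5: the one in-document figure on change without the drug.** Centre the on-treatment/baseline ratio on 1 − 0.174 = 0.826. The share with a 30% fall is Φ((ln 0.70 − ln 0.826)/SD) = Φ(−0.166/SD). This gives 20% at SD 0.2 and 42% at SD 0.8. The SD is again assumed, and the figure comes from another syndrome and from convulsive seizures.

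**Step 6: can the design inform about the effect it expects?** To exclude a 30% background at one-sided 0.025, 11 of 20 responders are needed. If the true share is 73% (16/22), the chance of this is 98%. Against a 40% background, 13 of 20 are needed and the chance is 86%. In the first earlier series of 11 patients, 64% became seizure-free and "the remaining 36% of subjects experienced greater than or equal to 75% reduction in seizure frequency".

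**Step 7: does the text claim what the design cannot give?** Sections II, III and V contain no rule that a given number of responders proves efficacy and no claim of confirmation. Section VIII speaks of efficacy conditionally. The background's wording and the objective in Section II differ in tone and do not contradict each other.

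**The case for a change.** The best case for the concern is that it asks for little. It does not demand a control arm or more patients, only that the objective match an uncontrolled design. The objective is fixed in the protocol, so the unseen SAP does not settle it. The placebo figure in the protocol's own background shows that change without the drug is real: centred on it, the background share is 20% to 42%, and 8 of 20 (lower limit 19.1%) would not exclude even the bottom of that range. If the true responder share were 50%, the chance of excluding a 30% background would be only 41%.

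All of that stands as a caution for whoever interprets the results. A moderate responder share from this study should not be read as proof of a drug effect, and regression to the mean is possible for patients who enter near the threshold.

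It does not amount to an error in the plan. The harm needs two things the protocol does not contain: a particular between-period variation, and a later report that overstates a moderate result. The same conditional could be raised against almost any uncontrolled before-after study. Further responder cuts, exact intervals and a statement on regression to the mean would be useful reporting, but they commonly sit in an SAP and would not remove the baseline bias.

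**Conclusion.** The concern does not hold. The objective names the question, and the protocol openly describes an uncontrolled group of at most 20 with no success criterion that this design would fail to meet. The modelled background at the 30% mark, 0.2% to 54%, is too wide to show that a moderate result would be uninterpretable, and the end that applies depends on an undocumented between-period variation. For an effect of the size in the earlier series, the design is informative.

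This rests on two readings. The study is taken to be uncontrolled because all patients receive ZX008 and no comparator appears. The 30% mark is taken as a goal and follow-up rule because no test is attached to it. Had the protocol set a responder count as proof of efficacy, the absence of a background share would be a real fault.

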# **III. SUBJECT SELECTION**

The study population will include pediatric and young adult patients seen by [name]., Ph.D. at MGH's Pediatric Epilepsy Clinic who were identified as candidates. The Principal Investigator (PI) will follow up to 20 patients with Sunflower Syndrome who will be taking ZX008.

# The inclusion criteria for enrollment in this study include:

- Subject is male or non-pregnant, non-lactating female, age 4 to 25 years, inclusive as of the day of the screening visit. Female subjects of childbearing potential must have a negative serum pregnancy test at screening. Subjects of childbearing or child-fathering potential must be willing to use medically acceptable forms of birth control, which includes abstinence, while in this study and for 90 days after the last dose of study drug.
- Subjects must have a diagnosis of Sunflower Syndrome, where seizures are not completely controlled by their current treatment plan.

- Subjects must experience seizures including absence seizures and/or generalized tonic-clonic seizures which involve seeking out a light source, staring at the light source, and waving one hand in front of their eye(s). Subject's must experience an average of 6 handwaving associated with absence seizures and/or generalized tonic-clonic seizures per week.
- Evidence of EEG in the medical history that shows generalized spike and wave discharges between seizures and a strong photoparoxysmal response during photic stimulation. Acceptable evidence includes a copy of the EEG trace, EEG report, or physician note that appropriately describes the EEG findings.
- All medications or interventions for epilepsy must be stable for at least 4 weeks prior to screening and are expected to remain stable until Month 3.
- Subject and/or parent/guardian has been informed of the nature of the study and informed consent has been obtained from the subject and/or legally responsible parent/guardian.
- Subject has provided assent in accordance with Institutional Review Board (IRB)/Ethics Committee requirements, if capable.
- Subjects parent/caregiver is willing and able to be compliant with diary completion, visit schedule, and study drug accountability.

# The exclusion criteria for enrollment in this study include:

- Subject has a known hypersensitivity to fenfluramine hydrochloride or any other ingredients in the investigational drug.
- Subject's etiology of seizures is a degenerative neurological disease.
- Subject is pregnant.
- Subject is not willing to comply with a method of birth control acceptable to the LPI (Licensed Physician Investigator) during the study and for 90 days following completion of the study.
- Subject is breastfeeding.
- Subject has a history of drug or alcohol abuse.
- Subject has pulmonary arterial hypertension.
- Subject has current or past history of cardiovascular or cerebrovascular disease, such as cardiac valvulopathy, myocardial infarction or stroke, or clinically significant structural cardiac abnormality, including but not limited to mitral valve prolapse, atrial or ventricular septal defects, patent ductus arteriosis, and patent foramen ovale with reversal of shunt. (note: bicuspid valve is not considered exclusionary, but may be

associated with the following diseases, which are exclusionary: coarctation of the aorta, Turner syndrome, supravalvular aortic stenosis, subvalvular aortic stenosis, patent ductus arteriosus, Sinus of Valsalva aneurysm, ventricular septal defect, Shone's complex, ascending aortic aneurysm, Loeys-Dietz syndrome, ACTA2 mutation familial thoracic aortic aneurysm syndrome, and MAT2A mutation familial thoracic aortic aneurysm syndrome).

- Subject has current or recent history of anorexia nervosa, bulimia, or depression within the prior year that required medical treatment or psychological treatment for a duration greater than 1 month.
- Subject has a current or past history of glaucoma.
- Subject has had an anoxic episode requiring resuscitation within 6 months of the screening visit.
- Subject has moderate or severe hepatic impairment. Asymptomatic subjects with mild hepatic impairment (elevated liver enzymes < 3x upper limit of normal (ULN) and/or elevated bilirubin <2x ULN) may be entered into the study after review and approval by the Medical Monitor in conjunction with the sponsor, in consideration of comorbidities and concomitant medications.
- Subject has severe renal impairment (estimated glomerular filtration rate <30mL/min/1.73m^2)
- Subject is receiving concomitant therapy with: centrally-acting anorectic agents; monoamine-oxidase inhibitors; any centrallyacting compound with clinically appreciable amount of serotonin agonist or antagonist properties, including serotonin reuptake inhibition; other centrally-acting noradrenergic agonists, including atomoxetine; or cyproheptadine. (Note: Short-term medication requirements for prohibited medications will be handled on a per case basis by the medical monitor.)
- Subject is receiving a dose of Epidiolex that is above the labeled dosing recommendations for that product. (20 milligrams/kilogram/day)
- Subjects is using an artisanal formulation of CBD
- Subject has been taking felbamate for less than 1 year prior to screening and/or does not have stable liver function and hematology laboratory tests, and/or the dose has not been stable for at least 60 days prior to the screening visit.
- Subject is known to be human immunodeficiency virus (HIV) positive.
- Subject is known to have active viral hepatitis (B or C).
- Subject is currently receiving an investigational medicinal product.

- Subject has participated in another clinical trial within the past 30 days (calculated from that study's last scheduled visit).
  Participation in non-treatment trials will be reviewed by the medical monitor.
- Subject is at imminent risk of self-harm or harm to others, in the investigator's opinion.
- Subject is unwilling or unable to comply with scheduled visits, drug administration plan, laboratory tests, other study procedures, and study restrictions.
- Subject is institutionalized in a general nursing home (i.e., in a facility that does not provide skilled epilepsy care).
- Subject does not have a reliable caregiver who can provide seizure diary information throughout the study.
- Subject has a clinically significant condition, or has had clinically relevant symptoms or a clinically significant illness in the 4 weeks prior to the Screening Visit, other than epilepsy, that would negatively impact study participation, collection of study data, or pose a risk to the subject.

